General Study Design: The proposed study is a prospective, randomized, clinical trial with attention control under the direction of the dual PIs, a behavioral scientist and a virologist. The study team is also made up of investigators from infectious diseases, mind-body medicine, geriatrics, and biostatistics. Subjects will be randomized to participation in an 8-week group MBSR course as the study intervention or to the Health Enhancement Program (HEP) as the active control arm. The study population will consist of 120 individuals, 50 years old or older, long-term (5 years on ART or longer) HIV-infected adults with well-controlled plasma viremia. Randomization will be stratified to achieve balanced distribution between the groups based on gender and study site. The experimental group will participate in the 8-week MBSR course followed by six, once-per-month booster sessions, and the control group will participate in HEP, a validated group attention control condition for MBSR maintaining subjects inert to mindfulness, with additional monthly educational meetings for

six months. Both groups will be evaluated using two sets of measures: biological markers associated with chronic inflammation (IL-6, CRP, sCD14, d-dimer) and measures of psychosocial stress (anxiety, depression, fatigue, and mindfulness). Subjects will be assessed at three time points: baseline, 8 weeks (immediately after completion of MBSR intervention), and 6-months post MBSR course (immediately after completion of booster sessions). We will use mixed linear and structural equation model to test study hypotheses.

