Intervention: Mindfulness-Based Stress Reduction (MBSR) Course: The MBSR course will follow the approved curriculum by the University of Massachusetts Medical School. Participants will attend 8 weekly sessions, 2.5 hours each, and a 5 hour silent retreat during the 6th week of the program. Two cohorts of MBSR sessions (in concurrence with HEP attentive control sessions) will be conducted in groups of 30 subjects each. Formal mindfulness meditation methods taught in the MBSR course include: Body Scan Meditation (a supine meditation), Gentle Hatha Yoga (practiced with mindful awareness of the body), Sitting Meditation (mindfulness of breath, body, feelings, thoughts, and emotions), and Walking Meditation. Informal Mindfulness Meditation Practices (mindfulness in everyday life) include: 1) awareness of pleasant and unpleasant events, and, 2) deliberate awareness of routine activities and events such as eating, weather, walking, and interpersonal communication. Daily home assignments include a minimum of 30 minutes daily formal mindfulness practices and 5-15 minutes informal practice, 6 days per week for the entire duration of the course. Course sessions will consist of discussions oriented around weekly homework assignments, including an exploration of obstacles, and development of self-regulatory skills and capacities. Monitoring for completion of course assignments and mindfulness practice will also be recorded on a weekly basis using a daily online log. [name] will facilitate the MBSR course. She has taught MBSR to a wide range of patients and health professionals since 2006, and is a Certified MBSR Teacher, the highest level of teacher recognition by the University of Massachusetts Center for Mindfulness. After completion of the 8-week MBSR course, subjects will meet 6 times monthly for a 1-hour refresher session. A monthly online log will be used to record frequency of practice over this 6-month period. Subjects will receive biweekly email reminders to log their practice adherence.

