Potential Challenges, Proactive Measures, Alternative Strategies: Although the HEP active control intervention provides the strongest RCT design, we are aware that it may also pose a challenge in observed outcomes if the effect size of our intervention is small. This is a plausible scenario for two reasons: (1) the attention effect of the active control intervention and (2) elements of the HEP intervention directly reducing psychosocial stress. To account for this possibility, statistical analysis will also include within subject differences. In addition, the sessions of HEP that could most influence stress reduction (i.e., physical activity)^{58,59} will be replaced by educational sessions. Elements such as the weather, and community illnesses associated with weather (i.e., colds, flu, etc.) may impact outcomes of the proposed study. To account for this potential impact, both arms of the study will take place concurrently. Both weekly sessions (one MBSR and another HEP) will take place during the same week in the exact same location (a conference room at Mount Sinai Hospital).

Participants and Recruitment: Subjects will be recruited at the Mount Sinai Health System in Manhattan, New York. In 2013, an integrated health system was created through the merger of Mount Sinai Medical Center and Continuum Health Partners. It is expected that the study will be able to recruit enough subjects at

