Aim 1: To assess the effect of MBSR on biomarkers of chronic inflammation in HIV-infected adults with well-controlled plasma viremia. The primary outcome for the analyses of treatment effectiveness will be IL-6 levels. We will use mixed linear models to assess the effect of the intervention on markers of inflammation. The model will include fixed effect terms for treatment group, time, and time-treatment interactions. In secondary analyses, we will similarly assess the effect of the intervention on secondary markers of inflammation (CRP, sCD14, d-dimer) using appropriate adjustments for multiple comparisons. If there are imbalances in patients’ characteristics across groups, statistical adjustment including these factors as covariates will be performed. All analysis will use an intent-to-treat principle. **Power Calculation:** Sample size calculations were based on the following assumptions: 1) mean baseline IL-6 of 2.0 pg/ml (SD:0.5)^{17,98}; 2) stable IL-6 levels in the control arm; 3) clinical significant effect of MBSR will be a net reduction of IL-6 of >0.5 pg/ml.^{98,99} Under these assumptions, a sample size of 100 patients (50 per group) will provide a power >80% using 2-sided test and a 0.05 significance level. One hundred and twenty study participants will be enrolled. Dropout rates reported in the literature for MBSR studies range significantly (range 0 to 48%, mean 10%). In order to lean on a conservative side a higher dropout rate of 15% is estimated for this study. With a 120 enrolled, a 15% dropout rate provides 102 completed participants. It is quite feasible to recruit 120 patients from this estimated eligible sample of 1,800 subjects at the three recruitment sites (requiring participation of ~7% of the eligible sample).

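### Cohort is in neither the randomisation strata nor the Aim 1 model, so chance cohort imbalance and any cohort-by-visit shift in IL-6 stay in the error term: a minor, cheaply removed loss of precision

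*Combined protocol and SAP*

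**What the plan says.** All of the relevant text is in section C (Approach) of the combined protocol and SAP.

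- **General Study Design:** "Randomization will be stratified to achieve balanced distribution between the groups based on gender and study site". No block size, allocation method or timing of randomisation relative to class start is given.
- **Intervention (MBSR course):** "Two cohorts of MBSR sessions (in concurrence with HEP attentive control sessions) will be conducted in groups of 30 subjects each". Two cohorts × two arms × 30 = 120, which matches the planned enrolment.
- **Potential Challenges after the HEP control arm:** the plan itself names the threat, "Elements such as the weather, and community illnesses associated with weather", and gives its remedy: "To account for this potential impact, both arms of the study will take place concurrently". The timetable follows: "Both weekly sessions (one MBSR and another HEP) will take place during the same week in the exact same location".
- **Aim 1:** "The model will include fixed effect terms for treatment group, time, and time-treatment interactions". Covariates enter only if patients' characteristics turn out to be imbalanced, in which case "statistical adjustment including these factors as covariates will be performed". Cohort is not mentioned there.

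The documents never call the cohorts successive. That is an inference: with one MBSR and one HEP session per week, two MBSR classes of 30 cannot run in the same weeks.

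**The concern.** If the cohorts run at different times of year, the change in IL-6 from baseline to a later visit may differ between them for reasons unrelated to treatment. Running the arms side by side exposes both to each season. It does not ensure that each arm has the same share of its subjects in each cohort, and it does not take seasonal variation out of the residual. Allocation within cohort would do the first, and cohort terms in the model would do the second. The plan has neither.

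A single time effect common to both cohorts averages over any cohort difference in change. A subject random intercept, if one is fitted, would absorb a constant difference in level between cohorts but not a difference in change, and change is what the group-by-time term measures. The covariate clause does not help: it is triggered by imbalance in patient characteristics, and cohort is a design factor.

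At stake are some precision in the primary comparison and a secondary practical matter, whether classes come out at the planned 30. This is not the question of clustering by class. Cohort is crossed with arm, so a cohort term removes noise.

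**Working it through.** **Inputs from the documents.** IL-6 SD 0.5 pg/ml (a baseline SD; no SD of change is given), target difference 0.5 pg/ml, 50 per group, two-sided 0.05, three recruitment sites, about 76% male.

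**Inputs assumed.** Equal-sized sites; the first 60 subjects form cohort 1; permuted blocks of 4; a between-cohort difference *s* in mean IL-6 change, common to both arms, of 0.1, 0.25 or 0.5 pg/ml.

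**1. The plan's own power figure.** Standard error = 0.5 × √(2/50) = 0.10. Power = Φ(0.5/0.10 − 1.96) = Φ(3.04) = 99.9%. The stated figure of more than 80% is therefore true as a lower bound; these inputs need only 16 per group for 80%.

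**2. Class sizes.** Allocation of 120 subjects over 6 gender-by-site strata was simulated 8,000 times.

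- Blocks of 4, cohort not a stratum: the first MBSR class has a 95% range of 28 to 32 and is exactly 30 in 35% of runs. In 10.7% of runs at least one cohort is 3 or more away from 30:30.
- Blocks of 6 or 8: the 95% range is 27 to 33.
- Blocks of 4 with cohort added as a further stratum: the 10.7% falls to 3.8%, but exactly 30 in the first class stays at 35%. An extra stratum alone does not deliver 30:30.

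**3. Chance shift in the arm contrast.** If cohort 1 splits *a* : 60 − *a* and cohort 2 mirrors it, the contrast moves by *s* × (2*a* − 60)/60. For a 32:28 split this is *s* × 4/60. At *s* = 0.25 it is 0.017 pg/ml and at *s* = 0.5 it is 0.033 pg/ml, against a standard error of 0.10 and a target of 0.5.

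**4. Residual variance.** Omitting a balanced two-level factor with difference *s* gives a total SD of √(SD² + *s*²/4). At SD 0.5 and *s* = 0.5 this is √(0.25 + 0.0625) = 0.559. Power is then Φ(0.5/(0.559 × 0.2) − 1.96) = Φ(2.51) = 99.4%.

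| *s* (pg/ml) | Variance rise, SD 0.5 | SE rise, SD 0.5 | Power, SD 0.5 | Power, SD 0.707 | Power, SD 0.892 |
|---|---|---|---|---|---|
| 0, or cohort in model | none | none | 99.9% | 94.2% | 80% |
| 0.1 | 1% | 0.5% | 99.9% | 94.1% | 79.9% |
| 0.25 | 6.25% | 3.1% | 99.8% | 93.6% | about 79% |
| 0.5 | 25% | 11.8% | 99.4% | 91.5% | 77.0% |

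The value 0.707 is the SD of change if visits are uncorrelated (0.5 × √2). The value 0.892 is the SD at which 50 per group has exactly 80% power. It is a deliberately harsh case, not a figure from the plan.

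**The case against.** The strongest reply is that concurrency already does the main job. Both arms meet every season in the same weeks and the same room, so season cannot favour one arm systematically. **That stands.** A reader might infer that the season safeguard fails and the treatment estimate is biased. The documents do not support this: imbalance between cohorts arises by chance, its expected effect is zero, and the standard error already covers it. For the same reason, the shift in step 3 and the wider interval in step 4 should not be counted as two separate harms. With near-balanced cohorts, leaving cohort out makes the interval slightly conservative, not invalid.

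A reader might also quote a much worse case: unrestricted allocation within strata would let the first class range from about 22 to 38, and a 38:22 split with *s* = 0.25 moves the contrast by 16/60 × 0.25 = 0.07 pg/ml. Stratification whose stated purpose is balance implies restricted allocation, so those figures should not be used.

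Three further replies have partial force.

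- The size of *s* is assumed throughout, and 0.5 pg/ml is as large as the whole target effect. The plan also assumes stable IL-6 in the control arm. This is correct, and it is why a range is shown; but the plan itself says that weather and related illness may affect outcomes.
- The plan already controls other noise through a single assay run, a fixed 3 to 6 pm draw and two averaged IL-6 draws per time point. These deal with assay, time-of-day and within-subject variation, but do not remove a seasonal shift.
- Allocation cohort by cohort may already be intended. The documents are silent, so this supports stating the method. It does not supply the missing model terms.

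**Conclusion.** The point holds as a cheap improvement of minor severity. Cohort is absent from both the strata and the Aim 1 model, so chance cohort imbalance and any cohort-by-visit shift remain in the error term.

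On the plan's own SD and target, the loss is at most about 0.5 percentage points of power for cohort differences up to 0.5 pg/ml. It is about 3 points in the harsh case of SD 0.892. The primary test is not endangered, and no one should read this as a finding that the trial is underpowered.

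The conclusion rests on the cohorts being successive, which is inferred from the timetable, and on an assumed range for the cohort difference. If the two cohorts in fact ran in the same weeks, the seasonal argument would fall away. The class-size range also depends on the assumed block size and site mix.

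**What to change.** **General Study Design:** state that allocation is 30:30 within each cohort of 60, stratified by gender and site, and give the method and timing. Preferably allocate each cohort in one batch after its baseline visits and before its first class. The 30:30 total must be imposed on the cohort as a whole, because blocks within small strata do not secure it.

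**Aim 1:** prespecify fixed effects for cohort and cohort-by-visit in the mixed model for IL-6 and for CRP, sCD14 and d-dimer. These terms are worth having even with exact allocation: balance alone leaves the cohort-by-visit variation in the residual, and the 15% dropout the plan expects can disturb the balance.

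**Cost:** a changed allocation list and three model degrees of freedom (one for cohort, two for cohort by three visits). With batch allocation, subjects learn their arm only shortly before classes start. The allocation change has to be made before the first cohort is randomised, and the model terms before outcome data are seen.

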were observed, but not sustained by the 12-month follow-up. Improvements in medical symptoms were also observed and sustained.^{41,44} In 2011, a study was conducted in Toronto with 78 MBSR participants and 39 treatment-as-usual controls. No differences were observed in measures of depression or anxiety, but improvements in a mindfulness scale were found.⁴⁵ More recently, Gayner and colleagues studied 117 participants (78 MBSR, 39 treatment-as-usual) and observed that MBSR participants had significantly lower avoidance and higher positive affect compared to controls.⁴³ [name] (consultant on this grant) and colleagues assessed the impact of MBSR on ART side effects. MBSR participants experienced a reduction in the frequency of symptoms associated with ART as well as a reduction in distress associated with those symptoms. Their study included 76 participants, 36 of which were in a wait-list control group with standard care.⁴² Although most of the data collected in these studies relates to psychological outcomes, there is suggestive evidence that the treatment leads to significant biological outcomes.

The field of psychoneuroimmunology has demonstrated a strong negative correlation between stress and immune system functioning in the general population.^{46,47} This correlation has been found in HIV disease with faster progression to AIDS associated with stressful life events.^{48,49} The connection between stress and immunity is mediated through the central nervous system.⁵⁰⁻⁵² Specifically, activation of the hypothalamic–pituitary–adrenal (HPA) axis and the sympathetic–adrenal–medullary (SAM) axis, results in production of hormones directly influencing the immune response. Cortisol, a glucocorticoid produced following HPA activation from stress, exerts immunosuppressive actions. Catecholamines, produced after SAM activation from stress, are also implicated in the immune response. The changes of the immune response caused by these hormones likely play a role in immune dysregulation and chronic inflammation observed in aging HIV-infected adults.^{53,54} MBSR is hypothesized to ameliorate clinical outcomes observed in these patients by reducing stress-induced hormones from the HPA and SAM axes.

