In this study, stress is hypothesized to exacerbate chronic inflammation in aging HIV-infected adults by stimulating production of hormones that directly impact the immune response. These changes directly impact biomarkers measured in the blood of these patients: IL-6, CRP, sCD14 and d-dimer. MBSR, by reducing the stress effect in these patients, could reduce levels of biomarkers associated with chronic inflammation. This conceptual model underlying the proposed study is graphically depicted in the Specific Aims.

B. Innovation

The proposed study will be the first to examine any form of alternative or complementary holistic therapy in older long-term HIV-infected persons with well-controlled plasma viremia.⁵⁵ It will also be the first MBSR study of HIV-infected adults to be conducted under the most rigorous RCT design with an active attention control condition that provides the same supportive climate of the MBSR group curriculum. From a translational medicine perspective, this study is innovative in that it examines a comprehensive set of biological markers specifically associated with chronic inflammation. No previous MBSR study has specifically targeted a set of biological markers that not only have been proven to be elevated in adults with HIV, but also been described as predictors of morbidity and overall mortality. This would be the first study to explore whether improvements in markers of psychosocial stress mediate the impact of MBSR on chronic inflammation.

This study is innovative in its effort to move HIV care beyond the current focus of virologic control, optimization of comorbid conditions, and encouragement of healthy lifestyle to include active interventions that can address the state of chronic inflammation and immune dysfunction underlying the early and accelerated aging process. Most bio-behavioral research in HIV to date has understandably focused on patients with poor adherence to HIV medication and treatment. This study is novel in its focus on highly adherent patients and the significant changes in profiles of biological markers associated with chronic inflammation documented in this cohort. The complementary medicine approach being studied has the potential to be integrated into the existing healthcare paradigm for HIV-positive persons.

C. Approach

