Potential Challenges, Proactive Measures, Alternative Strategies The key challenges when measuring the proposed 4 biological markers (IL-6, hsCRP, sCD14 and d-dimer) result from: 1) expertise and quality control of assay execution, 2) diurnal rhythm expression, and, 3) within subject variability.⁸⁸ To account for these potential challenges proactive measures have been established. First, and critically important, has been the establishment of collaboration with Drs. [name] and [name]. The level of expertise, experience and quality control provided by this lab assures reliability on recorded data. All frozen samples will be processed for execution of biological assays at a single run after completion of all collections. This measure controls for any potential variability during assay execution. The potential challenge of diurnal rhythm expression for all of the 4 biological markers will be addressed by strict serum collection in the three hour period between 3 pm and 6 pm. All blood samples for the entirety of the study will be collected in this three-hour time period and processed immediately, followed by immediate storage at a minus 80-degree freezer, assuring preservation of each marker. The concern of within subject variability is a key issue for IL-6 in particular.⁸⁹ For that reason, a critical approach measure has been established: two separate collections of blood for IL-6 measure at each time point, averaging the value for the two. Although it is recognized that this poses an additional level of demand on subjects, as they have to report to the study site twice for each of the three study time points, given the crucial role of IL-6 as the key biological marker, collecting two separate measures at each study time point provides the strongest level of reliability.

Measures of Psychosocial Stress and Mindfulness: Psychosocial measures will be assessed at 3 time points: baseline, after the 8 week course, and after the subsequent 6 month booster sessions.

The Patient Reported Outcomes Measurement Information System (PROMIS) is a system of highly reliable self-report measures, with substantial qualitative and quantitative evidence supporting validity, developed with funding from NIH.^{90,91} Two instruments have been selected from the PROMIS Neuro-QOL Item Bank v1.0 Short Forms: Anxiety and Fatigue (8 validated items each, for a combined instrument of 16 items).

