Aim 2: To explore whether changes in markers of psychosocial stress mediate the impact of MBSR on chronic inflammation. We will compare depression, anxiety, fatigue, and mindfulness scores among subjects in the active vs. control arm using a t-test or Wilcoxon test, as appropriate. The association between depression, anxiety, fatigue, and mindfulness scores with IL-6 (and other inflammatory markers) will be tested using the Pearson correlation coefficient. SEM analyses (using Mplus) will be based on the preliminary model depicted in Figure 1. We hypothesize that MBSR will impact inflammatory markers indirectly via effect on markers of psychosocial stress and mindfulness. Latent variables will be measured using a combination of factor scores (i.e., parceling) and items. Psychosocial stress will be measured with four factors (e.g., depression, anxiety, fatigue, mindfulness) allowing for the testing of specific pathways. This model will also include control variables. We will estimate parameters by using Weighted Least Squares Mean-Variance adjusted (WLSMV) estimator. The WLSMV method provides a robust estimation when sample size is moderate. Model fit will be evaluated based on various indices of exact and close fit: χ^2 (>0.05), the comparative fit index (CFI>0.90), the Tucker-Lewis fit index (TLI>0.90), the root mean squared error of approximation (RMSEA<0.05), and the weighted root mean square residual when using WLSMV (WRMR<0.90). To ensure consistent parameter estimates, we will estimate models including a latent class variable identifying the patterns of missingness. These analyses will be conducted using a latent class pattern mixture model. **Sample Size Calculations** were performed using the method presented by MacCallum et al.¹⁰⁰ Effect size in this approach is defined in terms of a null hypothesis and alternative hypothesis value of the root-mean-square error of approximation (RMSEA) index, which we hypothesized would be 0.05 (adequate fit) and 0.03 (good exact fit), respectively. We estimated that we would have, at minimum, 80 degrees of freedom, having a sample size of 120 subjects, and an error rate (alpha) of 0.05. Under these specified assumptions we will have >80% power.

Data Safety Monitoring Board (DSMB) Dr. [name] and Dr. [name] will serve on the DSMB for the study. The DSMB will meet twice yearly and [name] and [name] will attend the DSMB meetings.

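### Aim 2 can test mediation by anxiety, depression, fatigue and mindfulness scores, but cannot attribute it to stress or to the stress-hormone step, because neither is measured.

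*Combined protocol and SAP*

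**What the plan says.** **Mechanism (A. Significance).** The section describes cortisol and catecholamines as the link between stress and immunity, and then states: "MBSR is hypothesized to ameliorate clinical outcomes observed in these patients by reducing stress-induced hormones from the HPA and SAM axes". The conceptual model that closes the section adds: "MBSR, by reducing the stress effect in these patients, could reduce levels of biomarkers associated with chronic inflammation".

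**Question (C. Approach, Aim 2).** The aim is "To explore whether changes in markers of psychosocial stress mediate the impact of MBSR on chronic inflammation". B. Innovation lists this mediation question among the study's firsts.

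**Measures.**
- General Study Design lists "measures of psychosocial stress (anxiety, depression, fatigue, and mindfulness").
- Measures of Psychosocial Stress and Mindfulness names the instruments: "Two instruments have been selected from the PROMIS Neuro-QOL Item Bank v1.0 Short Forms: Anxiety and Fatigue", plus the BDI-II total score for depression and the FFMQ for mindfulness. All are given at baseline, after the 8-week course and after the 6-month booster period.
- Measurement of Biological Markers lists four assays: IL-6, CRP, sCD14 and d-dimer.

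**Place of mindfulness.** Aim 2 says "Psychosocial stress will be measured with four factors (e.g., depression, anxiety, fatigue, mindfulness) allowing for the testing of specific pathways", which puts mindfulness inside the stress construct. The hypothesis in the same paragraph says MBSR acts "indirectly via effect on markers of psychosocial stress and mindfulness", which names it as something separate. The instrument section gives the FFMQ a further role, as an indication of how far participants take up MBSR activities.

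**The concern.** The construct that carries the rationale, stress, has no measure of its own, and the hormonal step that follows it is not assayed. With mindfulness set aside, psychosocial stress rests on symptoms of anxiety, depression and fatigue. These may move with stress, but the documents give no evidence of how closely.

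Two readings of the result would then be unsafe:
- **Null result.** It would not separate the case where stress is not the path from the case where the symptom scores tracked stress poorly.
- **Positive result.** It could be described as mediation by stress when it shows mediation by distress symptoms. If the mindfulness factor drives it, it could instead reflect uptake of the training.

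The mindfulness problem has some basis in the plan's own literature. Of an earlier HIV trial with 78 MBSR participants and 39 usual-care controls, A. Significance reports: "No differences were observed in measures of depression or anxiety, but improvements in a mindfulness scale were found". If that pattern recurred, the component of so-called psychosocial stress that moved would be the one least like stress.

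**Working it through.** **1. Mechanism set against measurement.**

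| Step in the rationale | Measured? | By what |
|---|---|---|
| MBSR raises mindfulness | Yes | FFMQ |
| Stress falls | Not directly | Anxiety and fatigue short forms and BDI-II, as indicators |
| HPA/SAM hormones fall | No | No cortisol or catecholamine assay |
| Inflammation falls | Yes | IL-6, CRP, sCD14, d-dimer |

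Both lists of measures are given as complete, so the gaps in rows 2 and 3 are not the result of removed text.

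**2. The plan's own Aim 2 figure.** Aim 2 states power above 80% for RMSEA 0.05 (null) against 0.03 (alternative), with 80 degrees of freedom, N = 120 and alpha 0.05.
- Noncentrality is λ = (N − 1) × df × RMSEA².
- Null: 119 × 80 × 0.05² = 23.8. Alternative: 119 × 80 × 0.03² = 8.57.
- The 5th percentile of the noncentral chi-square under the null is 78.9. The probability of falling below it under the alternative is 25%, or 21% with 102 completers.

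The stated figure does not reproduce. That is a separate matter. For this point, what counts is that an RMSEA calculation concerns overall model fit and says nothing about power for an indirect effect.

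**3. What a stand-in score recovers (assumed model).** Let T be the arm and S stress, with S = aT + u and Var(u) = 1. Let the outcome depend on S with slope b, and let all of the effect pass through S. The stand-in is M = S + e with Var(e) = 1/r² − 1, so M correlates r with S within arm.
- Arm effect on M: a.
- Slope of the outcome on M given T: b × 1/(1/r²) = b r².
- Indirect effect through M: a × b × r², a share r² of the true one.
- Shares: r = 0.3, 9%; r = 0.5, 25%; r = 0.7, 49%; r = 0.9, 81%. A large-sample simulation gave 9%, 25%, 50% and 82%.

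**4. Illustrative power.** Assumptions: 102 completers (from Aim 1: 120 × 0.85), two equal arms, a 0.6 SD shift in stress, a standardized stress-to-IL-6 path of 0.4, and both paths required to reach p < 0.05. The last two columns use the average of three indicators, each correlating r with stress. Simulation error is about 1 to 2 points.

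| r | One stand-in score | Three pooled, independent errors | Three pooled, half the error variance shared |
|---|---|---|---|
| 0.8 | 61% | 76% | 69% |
| 0.7 | 46% | 70% | 55% |
| 0.6 | 29% | 60% | 41% |
| 0.5 | 17% | 46% | 26% |

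One stand-in score at r = 0.9 gives 74%. Perfectly measured stress (r = 1) gives only about 84–85%.

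Pooling helps because the average of three indicators with independent errors has correlation 1/√(1 + (1/r² − 1)/3) with stress. At r = 0.5 this is 1/√(1 + 3/3) = 0.71, so power is close to that of a single score at r = 0.7.

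**The case against.** The strongest reply is that Aim 2 does not ask about stress itself. It is exploratory, it asks about markers of psychosocial stress, and the plan says openly which markers these are and measures each at all three time points. The model is meant to allow specific pathways, so marker-by-marker reporting is possible. No aim in the text promises a test of hormones. **This stands.** A reader might infer that neither a positive nor a null Aim 2 result could answer anything; the documents do not support that. The limit applies to claims about stress itself and the hormonal mechanism.

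A second reply is that the power table models something simpler than the planned structural equation model, and that every input to it is assumed. This also stands. A reader might take the 17% for a single score at r = 0.5 as the trial's real power for mediation. It is not: the documents give no r, no expected shift in stress and no stress-to-IL-6 path.

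Third, the earlier trial without depression or anxiety differences is one of several. The same section also reports psychological symptom improvement that was not sustained at 12 months, lower avoidance with higher positive affect, and less distress from ART symptoms. So the literature does not show that these scores will stay flat. Nor can floor effects be claimed: entry requires no distress symptoms, but no baseline scores are given, and a perceived-stress scale would be open to the same doubt.

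Lastly, a perceived-stress scale is itself imperfect self-report, so some ambiguity in a null result would remain. Figure 1 and the Specific Aims diagram are not in the available text, so how stress enters the drawn model could not be checked.

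What these replies leave standing is the mismatch between the stated mechanism and the measures, and the inconsistent place of mindfulness.

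**Conclusion.** The point holds in a limited form. Aim 2 can show whether anxiety, depression, fatigue or mindfulness scores mediate an effect of MBSR on the inflammatory markers. It cannot attribute that mediation to stress or to the HPA/SAM axes. While mindfulness counts as part of psychosocial stress, a positive finding could reflect uptake of the training rather than lower stress.

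The gap in measurement rests on the documents alone. Its size does not: the r² shrinkage assumes that stress carries the whole effect, and the power table depends on assumed inputs, so both are illustrations and not estimates for this trial. The consequence is confined to the interpretation of an exploratory aim. The primary IL-6 comparison in Aim 1 does not depend on it.

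**What to change.** 1. Add one brief validated self-report scale of perceived stress at baseline, 8 weeks and 6 months, and name it the stress mediator in the Aim 2 model. It has to be in place from baseline, since it cannot be collected afterwards.
2. Keep anxiety, depression and fatigue, labelled as distress mediators.
3. Model mindfulness as its own mediator outside the stress construct, and bring General Study Design and both Aim 2 statements into line with this.
4. State that the hormone step in the rationale is not tested.
5. If no scale is added, limit the Aim 2 conclusion to distress symptoms and mindfulness.

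**Cost.** A short amendment and a few minutes of self-report at three assessments that already include questionnaires. No extra visit, blood draw or staff is needed. The downside is slightly more subject burden and one more mediator in an exploratory model. The fallback in item 5 costs only wording.
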